6.1.1. Intervention seminar

The intervention seminar will be a modified version of the “ECHT” seminar,^{9,10} consisting of three components: (a) three self-reflection exercises about participants’ own vulnerability to stigmatisation, stigmatisation risk in 24 different dermatological diseases, and participants’ reflection on which skin disease they could imagine living with the best and the least (30 min); (b) a lecture on skin diseases and stigma (20 min); and (c) an encounter with a person with psoriasis who shared their personal experience living with a VCSD with an emphasis on stigmatisation and answered questions of the participants (60 min). Apart from the patient encounter, seminar contents will be skin-generic.

6.1.2. Control seminar

The control seminar will be comparable to the intervention seminar in both structure and degree of required engagement/activity. The focus will lie on the participants’ health in the workplace consisting of: (a) a self-reflection phase, in which participants reflect on their own experiences with physical and psychological stress at work (30 min); (b) a lecture focusing on stress and stress management techniques (20 min); and (c) an e-learning tool on mental health for employees (60 min).

6.2. Participants

6.2.1. Number of participants

According to an a priori sample size calculation using G*Power¹¹ (F-tests for repeated measures ANOVA, within-between interaction) with the effect size obtained by Weinberger et al.¹⁰ (interaction effect for behavioural intentions: $\eta_p^2 = 0.02$), 82 participants are needed to obtain a power of 0.80 ($\alpha = 0.05$). To account for multiple testing and a potential drop-out rate of up to 20% at follow-up, we aim to include 120 participants in total.

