6.4.2. Statistical analysis

The statistical analyses will be conducted with the Statistical Package for the Social Sciences (SPSS v.27.0; IBM Corp., Armonk, NY). Descriptive statistics, i.e., absolute/relative frequencies and percentages for categorical variables and minimum, maximum, median, mean and standard-deviations for continuous variables, will be obtained for the total sample and subgroups of participants (e.g., by profession). The reliability of all questionnaires will be examined before conducting inference analyses, by calculating the Cronbach’s Alpha coefficients, considering $\alpha \geq 0.70$ as acceptable and $\alpha \geq 0.80$ as optimal.¹⁴ Assumptions of normality and sphericity will be checked by means of Shapiro-Wilk and Mauchly's Test of Sphericity, respectively.

Intervention effects on the primary outcomes will be analysed by means of 2 (Group: intervention, control) x 3 (Time: t0, t1, t2) repeated-measures analyses of variance (ANOVA). Subgroup analyses will be performed to assess potential differences between the professions. Intervention effects on the primary outcomes by profession will be analysed through 2 (Group: intervention, control) x 3 (Time: t0, t1, t2) x 3 (Profession: beauty, nurses, physical therapists) repeated-measures ANOVAs. The significance level will be established at a p-value ≤ 0.05 . Bonferroni correction for multiple testing will be applied. Effect sizes will be reported as η_p^2 , with $\eta_p^2 < 0.06$ indicating a small effect, $\eta_p^2 \geq 0.06$ indicating a medium effect and $\eta_p^2 \geq 0.14$ indicating a large effect.¹⁵ Post-hoc pairwise comparison will be used to further examine significant effects.

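### The power of 0.80 in section 6.2.1 does not fit the effect size it cites: on the natural reading of a partial eta-squared of 0.02, the planned sample gives about 0.39 to 0.48

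*Protocol*

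**What the plan says.** Section 6.2.1 of the protocol describes a G*Power calculation from the module "F-tests for repeated measures ANOVA, within-between interaction". The input is described as "with the effect size obtained by" an earlier controlled trial in future educators: an interaction partial eta-squared of 0.02 for behavioural intentions. The result is that "82 participants are needed to obtain a power of 0.80", with alpha 0.05. The section then adds: "To account for multiple testing and a potential drop-out rate of up to 20% at follow-up, we aim to include 120 participants in total".

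Section 6.4.2 fixes the matching analysis in SPSS, a "2 (Group: intervention, control) x 3 (Time: t0, t1, t2) repeated-measures analyses of variance (ANOVA"), with effects reported as partial eta-squared. It also says "Bonferroni correction for multiple testing will be applied", without naming the family of tests or the divisor.

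Neither section gives the correlation among repeated measures, the non-sphericity correction or the effect-size option used in G*Power.

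**The concern.** In a repeated-measures ANOVA, the partial eta-squared of the interaction is SS_interaction / (SS_interaction + SS_within-error). The within-person error term excludes stable differences between people, so a high correlation between time points has already made the error small and the eta-squared large. G*Power's default option for this module expects an effect size on a different scale, before that gain, and supplies the gain itself by dividing by (1 − rho). Entering an ANOVA partial eta-squared there credits the correlation a second time. The default also multiplies by the number of time points (3), where the ANOVA scale calls for that number less one (2).

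The power statement is the only quantitative basis given for the sample size. If it rests on this mismatch, the trial has far less than 80% power for the effect it names, and readers planning around or interpreting the behavioural-intentions result would be misinformed.

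**Working it through.** **Inputs from the protocol.** Partial eta-squared 0.02, alpha 0.05, target power 0.80, N = 82, drop-out up to 20%, recruitment target 120 (section 6.2.1). Two groups and three time points (section 6.4.2). Completers after drop-out: 120 × 0.8 = 96.

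**Inputs not in the protocol (inferred).** Correlation rho = 0.5, epsilon = 1, default effect-size option.

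**Common quantities.** f² = 0.02 / 0.98 = 0.02041 (f = 0.143). Numerator df = (2 − 1)(3 − 1) = 2. Denominator df = (N − 2) × 2. Power comes from the non-central F distribution with non-centrality lambda. N is rounded up to an even total.

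**1. Reproducing 82.** Default option: lambda = f² × N × 3 / (1 − rho).

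- N = 80: lambda = 0.02041 × 80 × 6 = 9.80, power 0.799.
- N = 82: lambda = 0.02041 × 82 × 6 = 10.04, power 0.809.

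The smallest even N is 82, as stated. With two groups and three times, the other correlations tried do not give 82:

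| rho | N |
|---|---|
| 0 | 160 |
| 0.3 | 112 |
| 0.4 | 96 |
| **0.5** | **82** |
| 0.6 | 66 |
| 0.7 | 50 |

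**2. The specification that matches an ANOVA partial eta-squared.** 'As in SPSS' option: lambda = f² × (N − 2) × 2.

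| N | lambda | power |
|---|---|---|
| 82 | 3.27 | 0.34 |
| 96 | 3.84 | 0.39 |
| 120 | 4.82 | 0.48 |
| 240 | 9.71 | 0.801 |

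So 80% power needs 240 completers. The 'as in Cohen' option, lambda = f² × N × 2, gives 238, so the choice between these two hardly matters.

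**3. Where the gap comes from.** Per participant, the default multiplies f² by 3 / (1 − 0.5) = 6 and the ANOVA scale by about 2. The threefold ratio is the product of 1 / (1 − 0.5) = 2 from the correlation and 3 / 2 = 1.5 from using m in place of m − 1. Read back onto the ANOVA scale, the lambda of 10.04 at N = 82 is a partial eta-squared of 10.04 / (10.04 + 160) = 0.059, nearly three times 0.02.

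**4. Rounding of 0.02.** The value has two decimals, so it could lie between 0.015 and 0.0249.

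| partial eta-squared | completers for 80% power | power at 96 |
|---|---|---|
| 0.015 | 320 | 0.30 |
| 0.02 | 240 | 0.39 |
| 0.0249 | 194 | 0.48 |

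**5. What 96 completers can detect with 80% power.** Partial eta-squared about 0.05 (0.049) at alpha 0.05. If Bonferroni is applied across the four primary outcomes of section 6.3.1 (an assumption), alpha is 0.05 / 4 = 0.0125, the detectable effect is about 0.068, and power for 0.02 is 0.21.

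All figures treat participants as independent. Section 6.1 assigns whole seminars to the arms. Any allowance for that is a separate matter and is not included.

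**The case against.** The strongest reply is that both halves of the argument involve inference. The protocol does not say which G*Power option or correlation was used, and the cited trial report is not at hand. If 0.02 had been defined on G*Power's default scale and rho were 0.5, then 82 would be right. That stands as a condition on the finding. But nothing in the protocol points that way. A value described as obtained in an earlier trial, as an interaction effect and as a partial eta-squared, is naturally ANOVA output, and section 6.4.2 adopts the same metric for this trial. The default settings are inferred from an exact match within the trial's own two-group, three-time layout.

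Four stronger readings are tempting and not supported:

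- **That power is one in three for this trial.** The 0.34 belongs to N = 82. The plan is 120 recruited, so 0.39 to 0.48 is the relevant range for 0.02.
- **That the trial is underpowered for every primary outcome.** The 0.02 concerns behavioural intentions only. The background section reports earlier significant effects on social distance, stereotypes and false assumptions but gives no sizes, so power for those outcomes cannot be derived from the protocol.
- **That power is 0.21 once multiplicity is handled.** This requires a divisor of four, which section 6.4.2 does not state. The correction might be meant for the post-hoc comparisons mentioned in the same paragraph.
- **That double use of the correlation explains the whole discrepancy.** It accounts for a factor of 2. The remaining 1.5 comes from the multiplier of 3 in place of 2.

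It can also be said that the increase from 82 to 120 provides a margin. It does not close the gap: even with no drop-out and no multiplicity adjustment, 120 gives 0.48.

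**Conclusion.** The point holds, conditionally. Assuming that 0.02 is a standard repeated-measures ANOVA partial eta-squared, the effect size, alpha, N and power in section 6.2.1 do not fit together. The requirement for 80% power is about 240 completers (194 to 320 over the rounding range), against 82 stated. Power for 0.02 on behavioural intentions at alpha 0.05 is 0.39 with 96 completers (0.30 to 0.48 over the rounding range) and 0.48 if all 120 complete. The cause, G*Power's default option with correlation 0.5 and epsilon 1, is a reconstruction and not a documented fact.

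The direction does not depend on the rounding of 0.02 or on which of the two ANOVA-scale options is used. A reader might infer that the trial must recruit 240 or more, or that a null result would be misread as evidence against the intervention. The documents establish neither. They show only that the stated power is not a property of this design for the effect named.

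**What to change.** Rerun the calculation with the 'as in SPSS' effect-size option. In section 6.2.1, state the option, epsilon and, if one is used, the correlation. Replace the 0.80 claim and keep the target of 120. Suggested text:

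> With 96 completers, power for an interaction partial eta-squared of 0.02 on behavioural intentions is about 0.39 at alpha 0.05. The effect detectable with 80% power is about 0.05 (about 0.068 at alpha 0.0125, if Bonferroni is applied across the four primary outcomes). These figures make no allowance for assignment by seminar.

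If the 0.02 was in fact on G*Power's default scale, say so and give the correlation assumed. The 82 can then be defended as it stands.

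The cost is one paragraph, with no change to design, endpoints or recruitment. The downside is that the stated power becomes much less favourable.

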6.3.1. Primary outcomes

- **Stereotype endorsement**^{9,12}: Agreement to negative stereotypes about people with psoriasis will be assessed using a scale consisting of 11 adjective pairs (e.g., unattractive – attractive). Participants were asked to mark the circle closest to the adjective they

considered to describe a person with psoriasis (range: 1–5). Scores will be averaged, with higher scores reflecting stronger endorsement of negative stereotypes.

- **Disease-related misconceptions^{9,12}:** To measure agreement with common misconceptions about psoriasis, participants will indicate their degree of agreement with 15 statements (e.g., “Psoriasis is contagious.”) on a 5-point Likert scale ranging from “strongly disagree” to “strongly agree”. Scores will be averaged, higher scores reflecting stronger endorsement of these misconceptions.
- **Desire for social distance^{9,12}:** Participants will rate their desire for social distance towards persons with psoriasis in nine situations (e.g., shaking hands) on a 5-point Likert scale ranging from “definitely not” to “definitely”. Scores will be averaged, higher scores reflecting a higher desire for distance.
- **Reported and intended behaviour¹³:** The Reported and Intended Behavior Scale consists of four items assessing the presence of behaviour (yes/no) in each of four contexts (living together with, working with, living nearby, and continuing a relationship with someone affected by a chronic skin disease) and four more items assessing intended behaviour in these contexts in the future, rated on a 5-point Likert scale ranging from “strongly disagree” to “strongly agree”. A sum score across the four “future behaviour” items will be calculated, with lower scores indicating more stigmatising behaviour.

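### 120 enrolled does not cover both a Bonferroni correction over the four primary outcomes and 20% drop-out: power per outcome is about 0.72 at the full drop-out allowance and 0.84 with none

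*Protocol*

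**What the plan says.** Protocol section 6.2.1 reports an a priori G*Power calculation ("F-tests for repeated measures ANOVA, within-between interaction") with a partial eta squared of 0.02 taken from an earlier trial in future educators. It gives 82 participants for power 0.80 at alpha 0.05. The next sentence reads: "To account for multiple testing and a potential drop-out rate of up to 20% at follow-up, we aim to include 120 participants in total". No step from 82 to 120 is shown, and no corrected alpha appears.

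The heading "6.3.1. Primary outcomes" covers four scales: stereotype endorsement, disease-related misconceptions, desire for social distance, and reported and intended behaviour. None is ranked above the others.

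Section 6.4.2 analyses the primary outcomes with repeated-measures ANOVAs of two groups by three time points, sets significance at 0.05, and adds: "Bonferroni correction for multiple testing will be applied". It does not say over how many tests.

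**The concern.** The calculation was run at an alpha that the analysis will not use if Bonferroni is applied across the primary outcomes. Section 6.2.1 offers 120 as the number that repairs this and absorbs up to 20% loss as well. Drop-out alone already takes 82 to 103 enrolled, so only 17 further participants are left to pay for the multiplicity correction.

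If that is too few, a non-significant result on a primary outcome would be read against a power of 0.80 that the design does not have at the planned level of loss.

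**Working it through.** **Inputs from the protocol.** Partial eta squared 0.02, alpha 0.05, power 0.80, drop-out up to 20% and 120 enrolled (6.2.1); k = 2 groups and m = 3 time points (6.4.2); four primary outcomes (6.3.1).

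**Inputs not in the protocol.** Correlation between repeated measures (rho) 0.5 and sphericity (epsilon 1). These are inferred because they return the stated 82.

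**Formula** (G*Power, within-between interaction, noncentral F):

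- f² = 0.02 / (1 − 0.02) = 0.0204, so f = 0.143
- lambda = f² × N × m × epsilon / (1 − rho) = 0.0204 × N × 3 / 0.5
- df1 = (k − 1)(m − 1) = 2; df2 = (N − k)(m − 1) = 2(N − 2)
- power = probability that a noncentral F(df1, df2, lambda) exceeds the critical F at the chosen alpha

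**Step 1: reproduce 82.** At N = 82, lambda = 10.04, df2 = 160 and critical F at 0.05 = 3.05, so power = 0.809. The smallest N that reaches 0.80 is 81, or 82 with equal groups. The other settings tried give a different N: rho 0 gives 160, 0.3 gives 112, 0.6 gives 66 and 0.7 gives 50; epsilon 0.75 gives 98; two time points give 100.

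**Step 2: drop-out alone.** 82 / 0.8 = 102.5, so 103 enrolled.

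**Step 3: add Bonferroni, same settings, equal groups.**

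| Tests | Alpha per test | Completers for 0.80 | Enrolled at 20% drop-out | Power at 96 completers |
|---|---|---|---|---|
| 1 | 0.05 | 82 | 103 | 0.871 |
| 2 | 0.025 | 96 | 120 | 0.801 |
| 3 | 0.0167 | 106 | 133 (132.5 rounded up) | 0.756 |
| 4 | 0.0125 | 112 | 140 | 0.722 |

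For four tests, N = 112 gives lambda = 13.71 and critical F = 4.47, hence power 0.805. Then 112 / 0.8 = 140.

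**Step 4: power of the stated 120 at alpha 0.0125, by drop-out.**

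| Drop-out | Completers | Power per outcome |
|---|---|---|
| 0% | 120 | 0.839 |
| 5% | 114 | 0.814 |
| 10% | 108 | 0.786 |
| 20% | 96 | 0.722 |

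The target of 0.80 holds while at least 112 of 120 complete, that is a loss of at most 8/120 = 6.7%.

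**Sensitivity to the inferred correlation** (96 completers, alpha 0.0125): power is 0.62 at rho 0.4 and 0.84 at rho 0.6. Those correlations would have given 96 and 66 rather than 82 in the protocol's own calculation.

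**The case against.** Four points can fairly be made against this.

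**The divisor is not stated.** Section 6.4.2 also contains profession subgroup ANOVAs and post-hoc pairwise comparisons, so Bonferroni might be meant for those, or the family might be defined in an SAP that is not shown. This stands as a limit on certainty. But section 6.2.1 ties multiplicity to the sample size, and the only family the protocol lists that could drive it is the four primary outcomes. Three tests would fail as well. If the correction were meant only for post-hoc comparisons, the shortfall would disappear, but the statement that 120 accounts for multiple testing would then have no defined meaning.

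**The protocol does not say that 120 gives 0.80 at a corrected alpha.** It attaches 0.80 to 82 participants at 0.05. This is correct. However, 0.80 is the only power target given, and 120 is presented as the adjustment of that calculation, so a reader will carry it over.

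**The loss may be smaller than 20%.** This stands: 0.72 belongs to the full allowance, and 0.84 applies if nobody is lost.

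**The correlation may exceed 0.5.** It may, but 0.6 is not consistent with the stated 82.

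Two stronger readings are tempting. Because two tests at 20% drop-out give exactly 120, a reader might infer that the sponsor corrected for two outcomes by mistake. Nothing in the protocol says so, and the synopsis also presents 120 as 30 per profession. A reader might also infer much lower power from the way the partial eta squared was entered in G*Power, or from the assignment of whole seminars to arms. Those are separate questions. The first depends on how the earlier trial computed its effect size, which the protocol does not show, and neither follows from the sentence examined here.

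**Conclusion.** The statement that 120 accounts for both multiple testing and up to 20% drop-out does not hold for four primary outcomes. Judged against the only power target the protocol gives, 120 is enough for four tests or for 20% drop-out, but not for the two together. It falls 20 short of the 140 needed, and power per outcome is 8 percentage points below target at the maximum planned loss.

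This rests on three assumptions: a Bonferroni divisor of four, which is the natural reading and not a stated one; correlation 0.5 with sphericity, inferred from the match to 82; and the protocol's effect size taken as entered. Severity is moderate. Estimates are not biased and the type I error is not inflated, because the correction itself is still applied.

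**What to change.** 1. In sections 6.2.1 and 6.4.2, state the Bonferroni family and the per-test alpha: four primary outcomes, 0.05 / 4 = 0.0125.
2. In section 6.2.1, replace the sentence on 120 participants with: *120 enrolled, at least 96 expected completers, power 0.72 to 0.84 per primary outcome across 20% to 0% drop-out at alpha 0.0125, assuming correlation 0.5 between time points and sphericity.* This removes the implication that 0.80 survives both adjustments.
3. If the sponsor intends a different family, name it and show the step from 82 to 120.

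This is a change of wording only, and enrolment stays at 120. The cost is a less favourable stated power. Keeping 0.80 at the full 20% loss would instead mean enrolling 140, which is 20 more participants.

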6.2.2. Inclusion and exclusion criteria

Eligibility will be checked through self-report. Inclusion criteria comprise:

- being 18 years or older;
- working as a hairdresser, cosmetologist, nurse or physical therapist or being at least in the second year of training for one of these professions;
- being able to consent autonomously and to speak and understand German
- having signed an Informed Consent Form.

6.3. Outcomes

Participants will be asked to report their sociodemographic information and fill in the following self-report questionnaires via the platform Unipark (<http://www.unipark.com>) or using pen and paper at three time points, immediately before (T0) and after (T1) participating in the seminar, and 3 months later (T2):

6.3.1. Primary outcomes

- **Stereotype endorsement**^{9,12}: Agreement to negative stereotypes about people with psoriasis will be assessed using a scale consisting of 11 adjective pairs (e.g., unattractive – attractive). Participants were asked to mark the circle closest to the adjective they

considered to describe a person with psoriasis (range: 1–5). Scores will be averaged, with higher scores reflecting stronger endorsement of negative stereotypes.

- **Disease-related misconceptions^{9,12}:** To measure agreement with common misconceptions about psoriasis, participants will indicate their degree of agreement with 15 statements (e.g., “Psoriasis is contagious.”) on a 5-point Likert scale ranging from “strongly disagree” to “strongly agree”. Scores will be averaged, higher scores reflecting stronger endorsement of these misconceptions.
- **Desire for social distance^{9,12}:** Participants will rate their desire for social distance towards persons with psoriasis in nine situations (e.g., shaking hands) on a 5-point Likert scale ranging from “definitely not” to “definitely”. Scores will be averaged, higher scores reflecting a higher desire for distance.
- **Reported and intended behaviour¹³:** The Reported and Intended Behavior Scale consists of four items assessing the presence of behaviour (yes/no) in each of four contexts (living together with, working with, living nearby, and continuing a relationship with someone affected by a chronic skin disease) and four more items assessing intended behaviour in these contexts in the future, rated on a 5-point Likert scale ranging from “strongly disagree” to “strongly agree”. A sum score across the four “future behaviour” items will be calculated, with lower scores indicating more stigmatising behaviour.

6.3.2. Secondary outcomes

- **Satisfaction with the seminar:** Participants’ satisfaction with the seminar will be assessed at T1 using twelve items addressing general satisfaction with the seminar and its scope, personal and occupational relevance, preparedness for similar situations at work, and whether they would recommend the seminar to a colleague.^{9,10} The statements will be rated on a 5-point Likert scale, ranging from “strongly agree” to “strongly disagree”, with lower scores indicating stronger satisfaction.
- **Blinding to study goal and group membership:** At follow-up, participants will be asked to describe what they thought was the goal of the study and to indicate whether they believed they were in the intervention group, the control group, or did not know which group they belonged to.

- **Port-Wine Stain:** As the intervention content is designed to be skin-generic, the questionnaires assessing stereotype endorsement, disease-related misconceptions and desire for social distance will be administered a second time with a focus on port-wine stain.
- **Emotional Responses:** A subscale of the Desire for Social Distance Scale¹² will be used to assess emotional responses to three images of persons with psoriasis and two images of persons with port-wine stain. Images are standardized with black background, and patients have consented to their images being used for research purposes. Participants will be asked to rate the extent to which they felt six emotions (blame, compassion, contempt, curiosity, disgust, pity) on a scale from 1 = “true” to 5 = “false” in response to the psoriasis and port-wine stain images, respectively.

